3.13.15 Total number of days on study drug

The total number of days a study participant received the study drug in EP0132 is defined as the day of last dose of BRV – date of first dose in EP0132 +1. The day of last dose of BRV is defined in [Section 3.13.14](#).

3.14 Plasma concentrations

For the calculation of descriptive statistics, a BRV plasma concentration below the Lower Limit of Quantification (LLOQ) is substituted by LLOQ/2. For diluted samples which are reported as <XX.X, the result will be substituted with LLOQ/2 based on the LLOQ level for the undiluted samples for the purposes of PK summaries. BRV plasma concentration results above the upper limit of quantification will not be substituted and will be regarded as missing in the PK summaries.

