9.1 Pharmacokinetics

Brivaracetam plasma concentrations will be summarized descriptively, by modal dose category in the Evaluation Period, at each FEV, YEV, and EDV or FV as applicable. Summaries will include n, geometric mean, geometric 95% CI, geometric coefficient of variation, arithmetic mean, SD, median, minimum, and maximum.

Descriptive statistics will be repeated, separately by modal dose category and categorized age group at EP0132 EV (see [Section 6.1](#)), and by modal dose category and weight at N01269 Baseline (<50kg at Baseline vs >=50kg at Baseline).

The statistics are calculated only if at least 2/3 of the individual data at a specific sampling point are above or equal to the LLOQ.

All samples should be pre-dose but in cases where the sample has been taken post-dose, the sample will be excluded from the summaries.

Plasma sample collection times and concentrations will be listed by study participant and visit including the plasma sample collection date and time, daily dose (mg), previous dose date and time, time since previous dose (hours) and plasma BRV concentration ($\mu\text{g}/\text{mL}$). The previous dose date and time refers to the most recent dose taken prior to the plasma sample collection, in most cases this will be the evening dose taken at home the day before the sample. The time since previous dose will be calculated as the difference between the plasma sampling time and the previous dose time. Daily dose refers to the most recent daily dose in mg prior to the sample as reported in the Study Drug Collection Dispensation and Administration eCRF.

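### Brivaracetam concentrations above the assay range are dropped from the PK summaries as missing, which can only pull the reported central values and maximum down

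*SAP*

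**What the plan says.** SAP 3.14 has three rules for concentrations outside the measurable range.

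- Low, undiluted: "a BRV plasma concentration below the Lower Limit of Quantification (LLOQ) is substituted by LLOQ/2".
- Low, diluted: "For diluted samples which are reported as <XX.X, the result will be substituted with LLOQ/2 based on the LLOQ level for the undiluted samples".
- High: "BRV plasma concentration results above the upper limit of quantification will not be substituted and will be regarded as missing in the PK summaries".

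SAP 9.1 lists what is computed from these values: "Summaries will include n, geometric mean, geometric 95% CI, geometric coefficient of variation, arithmetic mean, SD, median, minimum, and maximum". The summaries are by modal dose category at each visit, then again by dose and age group, and by dose and weight group. Two conditions apply: "The statistics are calculated only if at least 2/3 of the individual data at a specific sampling point are above or equal to the LLOQ", and "All samples should be pre-dose but in cases where the sample has been taken post-dose, the sample will be excluded from the summaries". SAP 9.1 also provides a listing of concentrations by participant and visit.

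Neither section asks for a count of results above ULOQ, a sensitivity summary that includes them, or a re-assay before a result is treated as missing.

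**The concern.** The two ends of the assay range are treated differently. A result below LLOQ is kept and given a value. A result above ULOQ is deleted, although what is known about it is that it exceeds every retained value measured against that limit. This is informative censoring, not missing data in the usual sense.

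The consequence follows without any model. Removing values larger than all those retained lowers the mean and geometric mean, cannot raise the median, and keeps the reported maximum at or below ULOQ. For right-skewed concentrations the SD falls as well. The tables by dose, age and weight are where a reader would look for groups with high exposure, and without a count the reader cannot tell that anything was removed.

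A smaller inconsistency sits beside it. A diluted sample reported as `<XX.X` is known only to lie below XX.X, yet it takes half of a different and lower limit.

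**Working it through.** **Inputs.** The rules and statistics come from SAP 3.14 and 9.1. The documents state no LLOQ, ULOQ, dilution factor, expected concentration, CV or censored share, so there is no plan figure to reproduce. Assumed here: log-normal concentrations, CV 40%, 60% or 80%, and a share p of 1%, 5% or 10% above ULOQ.

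**Results above ULOQ: formulas.** Let s = √ln(1 + CV²) and let z be the standard normal quantile at 1 − p, with Φ and φ the normal distribution function and density. Ratios are to the uncensored value.

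- Dropped: mean ratio = Φ(z − s)/(1 − p); geometric mean ratio = exp[−s·φ(z)/(1 − p)].
- Carried at ULOQ: mean ratio = Φ(z − s) + p·exp(s·z − s²/2); geometric mean ratio = exp{s·[p·z − φ(z)]}.

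**One case in full: CV 60%, p = 5%.** s = √ln 1.36 = 0.5545; z = 1.6449; φ(z) = 0.1031.

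- Dropped, mean: Φ(1.0904)/0.95 = 0.8622/0.95 = 0.908, so −9.2%.
- Dropped, geometric mean: exp(−0.5545 × 0.1031/0.95) = exp(−0.0602) = 0.942, so −5.8%.
- Carried, mean: 0.8622 + 0.05 × exp(0.9121 − 0.1537) = 0.8622 + 0.1067 = 0.969, so −3.1%.
- Carried, geometric mean: exp(−0.0116) = 0.988, so about −1%.
- Median: −3.4% when dropped, unchanged when carried.

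**Full range.** These are from a simulation of 1,000,000 draws. The closed forms agree within 0.1 percentage point.

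| CV | Above ULOQ | Mean, dropped | Geo. mean, dropped | SD, dropped | Mean, carried | Geo. mean, carried |
|---|---|---|---|---|---|---|
| 40% | 1% | −1.6% | −1.0% | −8.6% | −0.3% | −0.1% |
| 40% | 5% | −5.7% | −4.1% | −21.8% | −1.6% | −0.8% |
| 40% | 10% | −9.4% | −7.2% | −31.0% | −3.3% | −1.8% |
| 60% | 1% | −2.8% | −1.5% | −12.4% | −0.7% | −0.2% |
| 60% | 5% | −9.2% | −5.8% | −28.5% | −3.1% | −1.1% |
| 60% | 10% | −14.8% | −10.2% | −39.0% | −5.9% | −2.6% |
| 80% | 1% | −4.3% | −1.9% | −16.7% | −1.2% | −0.2% |
| 80% | 5% | −13.0% | −7.4% | −35.3% | −4.9% | −1.5% |
| 80% | 10% | −20.2% | −12.8% | −46.5% | −8.9% | −3.3% |

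If p = 0, every entry is zero.

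**Cell size.** Four modal dose categories (SAP Table 3-6) and five non-overlapping age bands (SAP 6.1) make 20 cells per visit. About 140 participants (SAP 2.4) average at most 140/20 = 7 per cell. One above-range result in such a cell is 1/7 = 14% of it, beyond the largest share in the table.

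**Diluted low results.** Let DF be the dilution factor and q the share of diluted `<XX.X` results in a cell. Take XX.X as DF × LLOQ. The geometric mean under the plan, divided by the geometric mean with XX.X/2, is DF^(−q). For DF from 2 to 10 this gives −0.7% to −2.3% at q = 1%, −3.4% to −10.9% at q = 5%, and −6.7% to −20.6% at q = 10%. These figures compare two substitutions; they do not measure error against the truth.

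A separate simulation did compare with the true values (CV about 53%, DF 5, q = 5%). The geometric mean fell about 10% and the arithmetic mean about 1.4%, while the median, 90th and 99th percentiles and maximum did not move. If the true value is uniform between 0 and DF × LLOQ, LLOQ/2 is above the truth with probability 0.5/DF: 25%, 10% and 5% for DF 2, 5 and 10.

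**The case against.** The strongest reply is that the rule may never be triggered. Protocol 8.5 tells participants not to take the morning dose before PK visits, and SAP 9.1 excludes post-dose samples from the summaries. Trough samples are where above-range results are least expected. The reference to dilution in SAP 3.14 and the back-up aliquot in Protocol 8.5 also suggest that over-range samples could be diluted and re-assayed, although the plan does not require it. This stands as a limit on size: nothing in the documents supports any particular censored share. It does not make the rule right when it is triggered.

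The second reply is that little depends on these tables. No PK endpoint appears among the objectives, Protocol 9.2 rules out hypothesis testing, and Protocol 9.4.2 sends any further PK modelling to a separate plan. This also stands, and it makes the point minor.

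Three stronger readings are tempting, and the documents do not support them.

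- A reader might infer that high exposures vanish from the report. They are lost from the summaries only; SAP 9.1 still lists individual concentrations with daily dose and time since the previous dose.
- A reader might infer that the dilution rule also removes the high tail. It acts on low results and leaves the upper quantiles and maximum alone. Nor is it always downward: if the true value is below LLOQ/2, for example after missed doses, LLOQ/2 is too high and XX.X/2 is higher still.
- A reader might take one diluted result in a cell of 12 as a 13% to 17% bias, since 5^(−1/12) = 0.874 and 10^(−1/12) = 0.825. That is again the gap between two substitutions, with an assumed dilution factor and frequency.

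The two-thirds condition does not worsen the problem. It limits results below LLOQ to one third of a summarised cell, which restrains low-end substitution.

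**Conclusion.** The point holds as a minor improvement. Treating results above ULOQ as missing removes them because they are high, and nothing elsewhere in the protocol or SAP corrects for it. Whenever the rule applies, the direction is known and the reported maximum is truncated.

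The size cannot be determined from the documents. The range in the brief rests on log-normality and on assumed CVs and censored shares, and zero is a plausible outcome for pre-dose samples. The trial's primary and secondary conclusions do not depend on it.

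The diluted-sample rule is a secondary matter of consistency. It mainly lowers the geometric mean and the minimum.

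**What to change.** In SAP 3.14:

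1. Include any result still reported as above ULOQ at the ULOQ value. Give the number of such results in each summary cell, and show the maximum as `>ULOQ` where one is present.
2. Replace a diluted `<XX.X` result by XX.X/2, which applies the SAP's own half-limit convention to the limit actually reported, or state why the undiluted limit is preferred.

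The cost is two sentences and a count column, with no new data. The drawback of the first change is that a value carried at the limit still understates the truth: at CV 60% with 5% above ULOQ, the mean stays about 3% low instead of 9%, and the geometric mean about 1% low instead of 6%. The count tells the reader when that matters.

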4 STATISTICAL/ANALYTICAL ISSUES

4.1 Handling of dropouts or missing data

4.1.1 Missing data

4.1.1.1 Seizure data

Six analyses of the proportion of study participants with absence seizure freedom will be conducted: 2 using 1-hour EEG, and 4 using seizure diaries. These analyses will be conducted as described in [Sections 3.13.2, 3.13.3, 3.13.4, 3.13.5, 3.13.6, and 3.13.7](#) respectively; for each of EEG, seizure diary, and seizure diary with modified criterion there is one analysis with imputation of non-response truncated at 24 months for participants who discontinue the study early, and one with no imputation of non-response for participants who discontinue the study early. There will be no missing data for the imputation analysis, as a study participant who does not meet all the criteria for absence seizure freedom will be regarded as not absence seizure free.

The proportion of 1-hour EEGs without absence seizure freedom will be artificially increased if some criteria have not been completed, hence every effort should be made to follow-up on missing criteria. All 1-hour EEGs with missing criteria should be discussed at DEMs, in order to determine the current stage of data management (ie, queried, response, resolution), the reason for the missingness (if available) and if additional sensitivity analysis are required. Also, note that 1-hour EEG listings will include information on which criteria have been met, not met, and are missing.

4.1.1.2 Adverse events

Missing data for AEs will be handled as follows:

- When relationship is not specified the AE is considered as related
- When intensity is not specified, the AE will be considered to be of severe intensity

4.1.2 Laboratory data

Laboratory values that are BLQ (eg, <X.X) will be imputed with value equal to the limit of quantification (ie, X.X) for the summarization of data. Laboratory values will be listed as received, prior to the substitution of any BLQ values.

4.1.3 Potential impact of Coronavirus Disease 2019 on dropouts or missing data

The COVID-19 pandemic may cause disruption in the conduct of ongoing clinical trials including treatment and study withdrawals, study participants missing study visits, and/or visits being performed remotely instead of at site. Sites will complete a COVID-19 Impact eCRF page in case a study participant was impacted by COVID-19 during the study. The COVID-19 Impact eCRF page will include the timing and impact of COVID-19, and the relationship to COVID-19 (ie, whether the study participant has confirmed/suspected COVID-19 infection, or whether the impact was due to general circumstances around COVID-19 without infection).

A study participant will be regarded as not absence seizure free based on EEG at a given visit if either the EEG was not performed or the EEG was performed but one or more criteria for absence seizure freedom were missing, regardless of whether the missing data was due to COVID-19. The impact of the COVID-19 pandemic for all endpoints will be assessed at DEMs,

and if considered significant, then sensitivity analyses may be conducted to assess the effect of the pandemic.

To assess the impact of COVID-19 vaccination on safety, selected summaries of TEAEs that are not exclusively related to COVID-19 vaccination will be presented, as described in [Section 10.2.1](#). In addition, a listing of COVID-19 vaccination related AEs will be produced, as described in [Section 10.2.2](#).

4.1.4 Handling of partial or missing dates

4.1.4.1 General imputation rule for incomplete dates

In all imputations for incomplete dates, the date of first dose of BRV refers to the date of first dose in EP0132. Where necessary for the calculation of derived variables, partial dates will be completed using the earliest calendar date based on the partial date provided. This rule is valid for all partial dates with the exception of the following:

- Date of birth (only year of birth is provided, and no imputation for the missing day and month will be conducted)
- Start and stop dates of medications
- Start date of AEs
- Start date of study medication

Completely missing dates will not be replaced (unless stated otherwise) and the corresponding derived variables will be set to missing.

4.1.4.2 Handling of partial date of birth

The full date of birth will not be presented. Only the year of birth will be presented for all study participants, and the day and month will not be imputed. Age will not be calculated from date of birth in this study. Age in months and years will be collected at each scheduled visit.

4.1.4.3 Handling of medications with partial or missing date

Any medications with incomplete start and end dates will be handled according to the following rules for classification as previous, concomitant, and follow-up. Such imputations will only be performed for these classifications and calculations; in the listings all data will be shown as recorded on the eCRF.

Imputation of partial start dates:

- For medications that are not ongoing from N01269:
 - If only the month and year are specified and the month and year of the first dose of study treatment in EP0132 is not the same as the month and year of the start date, then use the 1st of the month
 - If only the month and year are specified and the month and year of first dose of study treatment in EP0132 is the same as the month and year of the start date of the medication, then use the date of first dose of study treatment in EP0132
 - If only the year is specified, and the year of first dose of study treatment in EP0132 is not the same as the year of the start date, then use January 1st of the year of the start date

- If only the year is specified, and the year of first dose of study treatment in EP0132 is the same as the year of the start date of medication then use the date of first dose of study treatment in EP0132
- If the start date is completely unknown then use the date of first dose of study treatment in EP0132
- If the day and year are specified, but not the month, then treat the date as if the day and month are missing using the rules above
- For medications that are ongoing from N01269:
 - If only the year is specified, then use January 1st of the year of the start date
 - If the start date is completely unknown, then use the date of first dose of study treatment in N01269

Imputation of partial stop dates:

- If only the month and year are specified, then use the last day of the month, unless the participant has died during the month, in which case use the date of death
- If only the year is specified, then use December 31st of that year, unless the participant has died during the year, in which case use the date of death
- If the stop date is completely unknown, and the study participant has died during the study, use the date of death
- If the stop date is completely unknown, and the study participant has not died during the study, do not impute the stop date. Such medications will be considered to be ongoing and therefore concomitant unless the medication started in the Safety Period ([Section 3.3.2](#))
- If the full date of death is unavailable, then use the last day of the month of the date of death

In the event of ambiguity or incomplete data which makes it impossible to determine whether a medication was concomitant or not, the medication will be considered as concomitant.

4.1.4.4 Handling of adverse events with partial or missing date

Any AEs with incomplete onset dates will be handled according to the following rules for classification as pre-treatment AEs and treatment-emergent AEs. Such imputations will only be performed for these classifications; in the listings all data will be shown as recorded on the eCRF.

Imputation of partial AE onset dates:

- For AEs that are not ongoing from N01269:
 - If only the month and year are specified and the month and year of the first dose of study treatment in EP0132 is not the same as the month and year of AE onset, then use the 1st of the month
 - If only the month and year are specified and the month and year of the first dose of study treatment in EP0132 is the same as the month and year of AE onset, then use the date of the first dose of study treatment in EP0132.

- If only the year is specified and the year of the first dose of study treatment in EP0132 is not the same as the year of AE onset, then use January 1st of the year of the start date
- If only the year is specified, and the year of the first dose of study treatment in EP0132 is the same as the year of AE onset, use the date of first dose of study treatment in EP0132
- If the AE onset date is completely unknown then use the date of first dose of study treatment in EP0132
- If the day and year are specified, but not the month, then treat the date as if the day and month are missing using the rules above
- For AEs that are ongoing from N01269:
 - If only the month and year are specified and the AE is marked as ongoing from N01269, then use the 1st of the month
 - If only the year is specified, then use January 1st of the known year
 - If the AE onset date is completely unknown, then use the date of first dose of study treatment in N01269

There will be no imputation of partially or completely missing AE end dates as this is not required to determine if an AE is treatment-emergent.

In the event of ambiguity or incomplete data which makes it impossible to determine whether an AE was treatment-emergent or not, the AE will be considered as treatment-emergent.

4.1.4.5 Handling of study medication with partial or missing date

No imputation should be performed for missing study medication start dates. This field on the eCRF should not be partial or missing.

The last dose of study medication for participants who down-titrate will be the last dose during the Down-Titration Period; for participants who do not down-titrate, the last dose of study medication will be the date of either the EDV or the FV (unless the participant reports stopping study medication earlier). For partial or missing date of last dose of study medication on the Study Termination eCRF, the following imputation rules will be applied for the purpose of calculating overall exposure:

- If only the month and year are specified, impute the last dose date as the earliest of the last day of the month or the date of last contact reported on the Study Termination eCRF. If the participant has died during the month use the date of death if this is earlier
- If only the year is specified, impute the last dose date as the earliest of the last day of the year or the date of last contact on the Study Termination eCRF. If the participant has died during the year use the date of death if this is earlier
- If the last dose date is completely unknown on the Study Termination eCRF and no information could be obtained from data cleaning exercises, then use the date of last contact unless the participant has died during the year, in which case use the date of death. A review of the data for study participants with completely unknown last dose dates should be performed to ensure that the imputation does not result in an unrealistic value for duration of exposure

Imputed date of last dose dates should only be used for calculation of the duration of exposure. The date as recorded on the eCRF should be presented in study participant data listings (no imputed dates should be included in study participant data listings).

4.1.5 Handling of multiple assessments at a visit

If multiple EEGs, central laboratory assessments, ECGs or vital signs are recorded at the same visit, the first non-missing result (according to time of assessment recorded on the eCRF) will be used in summaries by visit. Assessments of PCS criteria will consider all assessments (scheduled and unscheduled) recorded during the period of interest.

4.2 Interim analysis and data monitoring

No formal interim analysis is planned; however, data may be reported prior to the completion of this study to support ongoing data cleaning, annual reports, regulatory submissions, and publications.

4.3 Multiple comparisons/multiplicity

No formal inferential statistical testing is planned; therefore, this section is not applicable.

4.4 Examination of subgroups

All outcomes will be evaluated by actual syndrome, as reported in N01269 (JAE/CAE); in addition, selected outcomes may be evaluated by COVID-19 Period (during pandemic vs post pandemic) if deemed appropriate. The impact of COVID-19 will be discussed at DEMs (as described in [Section 4.1.3](#)) and, if applicable, additional outputs may be presented. All evaluations will be descriptive.

5 STUDY POPULATION CHARACTERISTICS

5.1 Study participant disposition

5.1.1 Overall study participant disposition

The number of study participants in each of the SS and PKAS will be summarized for the ASPS.

An overall summary of disposition for study participants will present the number and percentage of study participants for the following categories:

- The number of study participants completing the study, including a sub-category for the number of study participants that were prescribed BRV after EP0132 (ie transitioned to another BRV study or a managed access program or converting to commercial BRV.)
- The number of study participants discontinuing the study and the primary reason for discontinuation

A study completer is defined as a participant who has met the criteria for study completion as described in [Section 3.3.5](#). Completion status will be determined from the Study Termination eCRF. All percentages will be relative to the number of study participants in the SS.

Study participant disposition will be listed on the ASPS and will include the following information: study participant status (screen failure, completed [including whether they were prescribed BRV after EP0132], or discontinued), date of informed consent/assent, date of first and last dose of study drug, date of study discontinuation, date of final contact, and primary

reason for study discontinuation (if applicable). For screen failures the date and reason for screen failure will be listed only.

Further study participant discontinuation information will be listed for participants in the SS who discontinued from the study including reason for discontinuation, the dose of study drug the study participant was on the day they were discontinued from study, the number of days for which this dose was received, and the total number of days on study medication. The derivation of these variables is detailed in [Sections 3.13.12, 3.13.14, and 3.13.15](#).

The following listings will be provided for all study participants: study participants who did not meet study eligibility criteria which will also specify each inclusion/exclusion criteria not met, and assignment of study participants to each of the analysis sets.

Additionally, the number of participants in the SS attending each scheduled study visit will be summarized. A listing of the study visits and associated visit dates will also be presented.

A separate summary of the number of participants in the SS starting and completing each 3-month period within the Evaluation Period will be summarized. A listing of the 3-month periods and associated period start and end dates will also be presented. Note if a participant completes the study (attends an FV) or discontinues from the study (attends an EDV) prior to the end of the 90-day period they are considered as not completing the 3-month period.

